11.3 Follow-Up Phase

The follow-up period begins immediately post-procedure (once the patient exits the clinic). Each subject will return for up to 7 follow-up visits (*see Section 5 Study Flow Diagram and Section 6 Schedule of Assessments*).

- Day 30 (\pm 7 days)
- Day 60 (\pm 7 days)
- Day 90 (\pm 7 days) – implant removal & repeat implant placement
- Day 120 (\pm 7 days)
- Day 150 (\pm 7 days)
- Day 180 (\pm 14 days) – implant removal, as applicable
- Day 365 (\pm 14 days)

The protocol-required follow-up assessment at each visit through Day 180 will consist of:

- Nasal obstruction/congestion questionnaire,
- SNOT-22 questionnaire, and
- Endoscopic grading and video recording.

Repeat implant placement procedure at Day 90

At the Day 90 follow-up visit, subjects with ethmoid sinuses with polyps (grade ≥ 1) will undergo repeat implant placement unilaterally or bilaterally. Repeat implant placement must not be performed in the ethmoid sinuses with no nasal polyps (grade < 1). All implants placed at Day 90 must be removed at Day 180 or may be removed earlier at the investigator's discretion.

If polypectomy is performed at the Day 90 follow-up visit, polyp grading must be done after polypectomy to qualify a given subject for repeat placement of the S8 Sinus Implant.

Note: The assessment of symptoms and pregnancy testing must be performed before repeat implant placement procedure.

Unscheduled visits

Subjects may come in for additional unscheduled office visits if necessary. Circumstances that may warrant additional visits include but are not limited to:

- Worsening of sinus symptoms,
- Sinus-related adverse events requiring medical evaluation, and/or
- Implant migration

The assessment at an unscheduled visit will consist of:

- Nasal obstruction/congestion questionnaire,
- SNOT-22 questionnaire, and
- Endoscopic grading and video recording.

12 CONCOMITANT MEDICATION

The study standardized medication regimen will be as follows:

- Leading up to the baseline procedure, there is a 30-day restriction for use of parenteral and injected steroids (e.g., Kenalog injection), and monoclonal antibodies (e.g., Dupixent, Nucala, Xolair) 1
- Leading up to the baseline procedure, a 14-day restriction for use of oral steroids, budesonide or other sinus steroid irrigations/rinses, nebulized steroids administered nasally or budesonide drops.
- After the baseline procedure, subjects will be encouraged to use saline rinses regularly through Day 365.
- After the baseline procedure, subjects will be required to use MFNS 200 mcg (two sprays in each nostril) once daily throughout the entire duration of the follow-up, unless the use of MFNS is not warranted clinically. Both the generic version of MFNS by Apotex or Novartis and the brand-name version by Merck (Nasonex) can be used.
- High-dose steroids (e.g., oral, parenteral, injections, budesonide or other sinus steroid irrigations, rinses or drops, nebulized steroids administered nasally) will be allowed during the study follow-up only if clinically necessary (see Section 13 *Medical and Surgical Interventions*).
- Orally-inhaled steroids for control of asthma will be permitted.
- If infection is suspected at any time during the study, treatment with antibiotics will be permitted.

- Use of monoclonal antibodies is prohibited during the 365-day follow-up period.
- To the extent possible, subjects will be maintained on stable regimens of leukotriene inhibitors and/or immunotherapy (e.g., Montelukast, Zafirleukast, Zileuton) for allergies through Day 365, if currently on such regimens; however, use of breath-powered or other methods of intranasal steroid delivery for allergies is not permitted during the study.
- Use of drug-eluting implants (PROPEL[®], PROPEL[®] Mini, PROPEL[®] Contour) is prohibited during the baseline procedure and throughout the 365-day follow-up period, unless placed immediately following RESS performed in the operating room setting.

All sinus-related and AE-related medications will be recorded in EDC, including their full brand/trade or generic names (whichever prescribed), dose, frequency, indication, start and end dates. Each AE will be coded using the Medical Dictionary for Regulatory Activities (MedDRA) and presented based on the system organ class (SOC) and preferred term.

13 MEDICAL AND SURGICAL INTERVENTIONS

Subsections below describe the rescue treatments consisting of medical and surgical interventions that will be allowed during the study follow-up based upon subject's symptomatic and endoscopic outcomes.

13.1 Medical Intervention

During study follow-up, high-dose steroids (e.g., oral, parenteral, injection, budesonide or other sinus steroid irrigations, rinses or drops, nebulized steroids administered nasally) may be used as a medical intervention in cases where a clinically significant increase or persistence in ethmoid sinus polyposis occurs, coupled with subject complaint of sinusitis symptoms that cause subject to request intervention.

If oral steroids are required for reasons other than, and not including, ethmoid sinus polyposis, a regimen is allowed. In either case, oral steroid intervention will be noted on the medication and follow up CRFs (see Section 16.5 *Handling Steroid or Surgical Interventions*).

13.2 Surgical Intervention

During study follow-up, surgical intervention (e.g., in-office polypectomy, RESS) may be required in cases where a clinically significant increase or persistence in ethmoid sinus polyposis occurs, coupled with subject complaints of sinusitis symptoms that cause subject to prefer sinus surgery.

Note: Subjects requiring medical or surgical interventions will be followed through the end of the study.

14.2 Classification of Adverse Events

Severity of event

Sponsor will be responsible for determining whether an AE is expected or unexpected based on the nature, severity, or frequency of the event as previously described in the risk management documents for the investigational product. TEAE, SAE, SAR, SUSAR, UADE and USADEs are defined in *Section 3 Definitions of Terms*.

Relationship of adverse event

An adverse event related to the use of study implant, which includes AEs resulting from insufficient or inadequate instructions for use, deployment, implantation, installation, or operation, or any malfunction of the investigational medical device. This also includes any event resulting from user error or from intentional misuse of the implant. [BS EN ISO 14155]

Based on the 21 CFR 312 and BS EN ISO 14155, the relationship of all AEs to the implant will be categorized into:

- *Related*: There is clear evidence to suggest a causal relationship, and other possible contributing factors can be ruled out. The clinical event, including an abnormal laboratory test result, occurs in a plausible time relationship to drug administration and cannot be explained by concurrent disease or other drugs or chemicals. The response to

withdrawal of the drug (dechallenge) should be clinically plausible. The event must be pharmacologically or phenomenologically definitive.

- *Possibly-related*: There is some evidence to suggest a causal relationship (e.g., the event occurred within a reasonable time after administration of the trial medication). However, other factors may have contributed to the event (e.g., the participant's clinical condition, other concomitant events). Although an AE may rate only as "possibly related" soon after discovery, it can be flagged as requiring more information and be updated, as appropriate.
- *Unlikely-related*: A clinical event, including an abnormal laboratory test result, whose temporal relationship to drug administration makes a causal relationship improbable (e.g., the event did not occur within a reasonable time after administration of the trial medication) and in which other drugs or chemicals or underlying disease provides plausible explanations (e.g., the participant's clinical condition, other concomitant treatments).
- *Not-related*: The AE is completely independent of study drug administration, and/or evidence exists that the event is definitely related to another etiology. There must be an alternative, definitive etiology documented by the investigator.

Any AE that is determined by a participating investigator to be directly related (related and possibly-related) to the implant-procedure, device, or drug will be categorized as implant-related.

For implant-related AE (anticipated or unexpected/unanticipated), sponsor may request source documentation to confirm the relationship of the AE/SAR to the implant and may review such AE with an independent otolaryngologist, as needed.

Note: The occurrence of a diagnostic or elective surgical procedure for a pre-existing condition, unless the condition becomes more severe or increases in frequency, would not be considered implant-related.

Severity of adverse event

Severity of AEs will be graded per 21 CFR 312 as follows:

- *Mild*: If an AE requires minimal or no treatment and does not interfere with the participant's daily activities.
- *Moderate*: If an AE results in a low level of inconvenience or concern with the therapeutic measures. Moderate AEs may cause some interference with functioning.
- *Severe*: If an AE interrupts a participant's usual daily activity and may require systemic drug therapy or other treatment. Severe AEs are usually potentially life-threatening or incapacitating.

14.3 Guidelines for Reporting of Adverse Events

Adverse event reporting

All AEs, regardless of seriousness or relationship to the implant, will be recorded in EDC and will include event description, date of onset, investigator's assessment of severity, relationship to investigational product, and date of resolution/stabilization of the event. All AEs occurring while on study must be documented appropriately regardless of relationship. All AEs will be followed through end of the study.

Any preexisting medical condition that is present at the time of screening will not be reported as an AE. The occurrence of a diagnostic or elective surgical procedures for a pre-existing condition will not be recorded as an AE, unless the condition become more severe or results in an AE

Whenever possible, diagnosis or single syndrome should be reported instead of symptoms. The investigator should specify the date of onset, severity, action taken with respect to implant, corrective treatment/therapy given, additional investigations performed, outcome, and his/her opinion as to whether there is a reasonable possibility that the AE was caused by the implant.

Changes in the severity of an AE will be documented to allow an assessment of the duration of the event at each level of severity to be performed. AEs characterized as intermittent require documentation of onset and duration of each episode.

The investigator should take appropriate measures to follow all AEs until resolution or until progression has been stabilized, to ensure the safety of the subjects. If the AE continues beyond the last planned visit per protocol, investigators should follow the subjects until AE resolution; stabilization and safety data will be recorded in the patient medical records.

When subject participation is prematurely discontinued, every attempt should be made to continue to collect safety data in the patient's medical records.

Serious adverse event reporting

All AEs that meet the criteria of an SAE must be reported to the sponsor based on the following timeline:

Type of Report	Reporting Schedule
Serious adverse event or Serious Suspected Adverse Reaction	Within 24 hours after becoming aware

The investigator will report the above to the reviewing IRB per the IRB's guidelines.

All SAEs will be followed until satisfactory resolution; until the investigator deems the event to be chronic or the adherence to be stable. Other supporting documentation of the event may be requested by the sponsor and should be provided as soon as possible.

Drug and device serious adverse event reporting

The study sponsor is responsible for conducting an evaluation of all ADE/SAR throughout the study duration. Since S8 Sinus Implant is a single-entity combination product, the sponsor shall report to the FDA all device-related UADE within 10 working days and all SAE and SUSAR within 15 calendar days after the sponsor deems the adverse event to be reportable. Sponsor is also responsible to notify all reviewing IRBs and participating investigators within 10 days after such determination is made. Thereafter the sponsor shall submit any additional reports concerning the effect as FDA requests. The sponsor will notify FDA of any unexpected fatal or life-threatening AE/SAR as soon as possible but in no case later than 7 calendar days after the sponsor's initial receipt of the information.

15 SAFETY INSTRUCTIONS

15.1 Contraindications

The S8 Sinus Implant is contraindicated in patients with:

- Suspected or confirmed intolerance to mometasone furoate.
- Known hypersensitivity to lactide, glycolide, or caprolactone copolymers

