
Eligibility Criteria
	
Key inclusion criteria:
 
 • Confirmed diagnosis of CS with nasal polyps. Per the 2016, “International Consensus Statement on Allergy and Rhinology” definition, patient must have ≥ 12 weeks of: 
 ○ Two or more of the following symptoms: 
 ▪ Mucopurulent discharge (rhinorrhea or postnasal drip) ▪ Nasal obstruction and congestion ▪ Decreased/absent sense of smell ▪ Facial pressure/pain ○ And one or more of the following findings: 
 ▪ Evidence of inflammation on paranasal sinus examination or computed tomography ▪ Evidence of purulence coming from paranasal sinuses or ostiomeatal complex ○ And presence of polyps. • Previous ESS including bilateral total ethmoidectomy at least 90 days prior to screening. • Patient must have evidence of bilateral ethmoid sinus polyps (grade ≥ 2 on each side) • Ethmoid sinus anatomy is amenable to bilateral placement of the S8 Sinus Implant (20 mm nominal length, 7 mm compressed diameter) 
Key exclusion criteria:
 
 • Extensive ethmoid sinus polyps (grade 4 on at least one side) • Extensive adhesions/synechiae (grade 3 or 4) • Oral-steroid dependent condition • History of allergy or intolerance to corticosteroids or mometasone furoate • Physical obstruction that would preclude access to or placement of the S8 Sinus Implant in the middle meatus • Evidence of acute sinusitis (AS), invasive fungal sinusitis or another disease or condition expected to compromise survival or ability to complete assessments during the 180-day follow-up period • Use of parenteral and injected steroids (e.g., Kenalog injection) 30 days prior to the baseline procedure • Use of monoclonal antibodies (e.g., Dupoxent, Nucala, Xolair) for treatment for asthma, allergies or nasal polyps 30 days prior to the baseline procedure
------------------------------------	--

	
 Use of oral steroids, budesonide or other sinus steroid irrigations/rinses, nebulized steroids administered nasally or budesonide drops 14 days prior to the baseline procedure

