The S8 Sinus Implant is composed of a blend of two different ratios of a synthetic bioabsorbable co-polymer, poly(L-lactide-co-glycolide) with different lactide/glycolide ratios. The implant has a coating containing mometasone furoate (active ingredient), a synthetic corticosteroid with anti-inflammatory activity. The chemical name is 9 α , 21-dichloro-11 β ,17 α -dihydroxy-16 α -methylpregna-1,4-diene-3,20-dione 17-(2-furoate), with the empirical formula C₂₇H₃₀Cl₂O₆, and a molecular weight of 521.43 g/mol. The drug is embedded in a bioabsorbable polymer matrix containing poly-(DL-lactide-co-glycolide) and polyethylene glycol (inactive ingredients) which provides for gradual release of the drug. This top coating is designed to provide a controlled release of mometasone furoate over the course of 90 days.

Crimper and delivery system

The implant comes pre-assembled in a crimper. The crimper holds the implant during shipping and works in concert with the delivery system to crimp and load the implant. The delivery system is designed to be single-handed, allowing the physician to place the implant under endoscopic guidance.

The delivery system is designed to provide access to the ethmoid sinus and controlled accurate deployment of the implant. The delivery system comprises the thumb and finger rests, the seeker and a cup (**Figure 3**). The seeker is extended by pushing with the thumb rest to load the implant onto the delivery system. The tip of the delivery system has a curvature of 10° to facilitate endoscopic placement.

[figure not shown]

Figure 3. Delivery system

General instructions for placement

The S8 Sinus Implant must be placed according to the prescribing information. To summarize, the S8 Sinus Implant is crimped and loaded by introducing the delivery system's seeker tip into the center of the implant, depressing the finger rests to extend the seeker and allowing the cup to capture all legs of the implant. For endoscopic placement, the thumb rest is pressed again to release the implant from the distal tip of the seeker into the ethmoid cavity. Upon release, the S8 Sinus Implant expands radially to conform to and dilate the sinus tissue. The delivery system is then retracted out of the patient. Final placement is confirmed by endoscopic visualization. The position of the S8 Sinus Implant can be adjusted after placement using the seeker on the delivery system.

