10.2 Eligibility Criteria

To be enrolled in the study, patients must meet all of the following inclusion criteria and none of the following exclusion criteria.

Inclusion criteria

- a. Patient has provided written informed consent using a form approved by the reviewing institutional review board (IRB) and sponsor.
- b. Patient is ≥ 18 years of age.
- c. Patient is willing and able to comply with protocol requirements.
- d. Patient has a confirmed diagnosis of CS with nasal polyps, as defined in the 2016 “International Consensus Statement on Allergy and Rhinology”.
- e. Patient has undergone prior ESS including bilateral total ethmoidectomy at least 90 days prior to screening.
- f. Patient has evidence of bilateral ethmoid sinus obstruction due to polyposis warranting intervention (polyp grade ≥ 2 on each side).
- g. Patient is able to tolerate daily use of Mometasone Furoate Nasal Spray (MFNS).
- h. Patient is able to tolerate topical/local anesthesia.
- i. In the opinion of the investigator, patient’s ethmoid sinus anatomy is amenable to in-office bilateral placement of the S8 Sinus Implant (i.e., able to pass into the middle meatus on both sides the S8 Sinus Implant with 20 mm in nominal length and 7 mm in compressed diameter).
- j. Female patients of reproductive potential must not be pregnant or nursing and must agree to not become pregnant during their participation in the study.
- k. Female patients of childbearing potential must agree to use consistent and acceptable method(s) of birth control during their participation in the study.

Exclusion criteria

- a. Patient has extensive ethmoid sinus polyp grade (grade 4 on at least one side).
- b. Patient has extensive adhesions/synechiae (grade 3 or 4).

- c. Patient has used parenteral and injected steroids (e.g., Kenalog injection) during 30 days prior to the baseline procedure.
- d. Patient has used oral steroids, budesonide or other sinus steroid irrigations/rinses, nebulized steroids administered nasally or budesonide drops during 14 days prior to the baseline procedure.
- e. Patient has oral-steroid dependent condition such as chronic obstructive pulmonary disease (COPD) or asthma.
- f. Patient has known history of allergy or intolerance to corticosteroids or mometasone furoate.
- g. Patient has used monoclonal antibodies for asthma, allergies or nasal polyps (e.g., Dupixent, Nucala, Xolair) during 30 days prior to the baseline procedure.

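### Section 15.1 contraindicates the implant in known copolymer hypersensitivity, but no eligibility criterion in section 10.2 screens for it

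*Protocol*

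**What the plan says.** **Contraindications (Protocol 15.1).** There are two. One concerns the drug: "Suspected or confirmed intolerance to mometasone furoate". The other concerns the implant material: "Known hypersensitivity to lactide, glycolide, or caprolactone copolymers".

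**Eligibility (Protocol 10.2).** The lists are decisive by their own terms: "To be enrolled in the study, patients must meet all of the following inclusion criteria and none of the following exclusion criteria". The only allergy criterion is exclusion f: "Patient has known history of allergy or intolerance to corticosteroids or mometasone furoate". The key exclusions in the Protocol Summary (section 4) carry the same content: "History of allergy or intolerance to corticosteroids or mometasone furoate".

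**What follows from eligibility (Protocol 4, Study Design).** Subjects who meet all the eligibility criteria go on to bilateral in-office placement.

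**Composition (Protocol 7.2).** The implant body is a blend of "a synthetic bioabsorbable co-polymer, poly(L-lactide-co-glycolide) with different lactide/glycolide ratios". The drug sits in a coating matrix of "poly-(DL-lactide-co-glycolide) and polyethylene glycol (inactive ingredients").

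The SAP has no eligibility list. Its section 3.0 says only that eligible subjects receive bilateral placement.

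**The concern.** Two parts of the protocol give different answers for the same patient. On section 10.2, someone with a known lactide/glycolide copolymer hypersensitivity qualifies. On section 15.1, that person should not receive the implant. The protocol did turn its drug contraindication into an exclusion, so a reader of section 10.2 could take the allergy check to be complete.

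The stake is patient safety. The exposure is to the named material itself, and it can recur: two implants at baseline and up to two more at Day 90. The trial's sole objective is the safety of repeat placement, so the entry rule and the contraindication list should agree.

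**Working it through.** There is no plan figure to reproduce. The check is a comparison of the sections.

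**Step 1. Does any listed criterion cover copolymer hypersensitivity?**
- Inclusion a to k is 11 criteria. The nearest are g (tolerates mometasone nasal spray), h (tolerates topical or local anesthesia) and i (anatomy suits the implant). None concerns the implant material. Result: 0 of 11.
- Exclusion a to r is 18 criteria. Exclusion f is limited to corticosteroids and mometasone furoate. Exclusion i concerns physical obstruction, and exclusion m concerns severe disease threatening survival or completion of assessments. Result: 0 of 18.
- The Protocol Summary lists key criteria only, and none of them names a polymer.

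**Step 2. Is the patient exposed to what the contraindication names?**

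| Named in 15.1 | In the 7.2 composition? | Covered by 10.2? |
|---|---|---|
| Lactide copolymer | Yes, body and coating | No |
| Glycolide copolymer | Yes, body and coating | No |
| Caprolactone copolymer | Not listed | No |
| Mometasone furoate | Yes, coating | Yes, exclusion f, in different words |

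The eligibility gap rests on the first two rows.

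**Step 3. Is there a later check?** At Day 90, sections 4 and 11.3 make repeat placement depend on polyp grade and allow the subject to decline. Symptom assessment and pregnancy testing must come before it. Nothing there refers back to section 15.1. The maximum is 2 implants at baseline + 2 at Day 90 = 4 implants over two placement occasions, which agrees with the up to four observations per patient in section 16.4.

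**Step 4. The two separate wording differences.**
- *Caprolactone.* The word occurs only in section 15.1. The documents do not show whether it is surplus there or missing from section 7.2.
- *Mometasone.* Section 15.1 reaches suspected as well as confirmed intolerance, while exclusion f requires a known history. Inclusion g narrows this difference in practice, because it requires tolerance of a mometasone spray, but the two texts still differ.

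**Step 5. Effect on the statistics.** The sample size rests on clinical judgment and the expected number of repeat placements (Protocol 16.1, SAP 7.2). The analysis population is everyone who received the implant (Protocol 16.6, SAP 5.0). Neither depends on this point.

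**The case against.** The strongest reply is that the contraindication is already in the protocol. Section 17.3 requires investigators to follow the protocol. Section 10.1 limits the population to patients for whom placement is medically suitable, section 11.2 ties placement to the prescribing information, and section 17.2.1 trains sites on both the protocol and the package insert. On this view, a rule in section 15 is simply not repeated in section 10.2.

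Much of that stands. A reader might infer that the protocol permits these patients to be implanted; it does not, because section 15.1 says otherwise. What remains is that none of these safeguards is a listed, checkable eligibility criterion, while section 10.2 presents its lists as decisive.

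Three other stronger readings lack support:
- *That the caprolactone mismatch helps to admit contraindicated patients.* It cannot. An extra named polymer only widens the contraindication, and section 15.1 does not say that the implant contains caprolactone.
- *That the screening form copies section 10.2 and so omits the check.* Neither the screening form nor the package insert is in the documents, so this is unknown.
- *That the safety data would be distorted by a definite amount.* One subject would be 1/50 = 2% of the planned treated population, but that is the arithmetic of a hypothetical subject. The documents give no prevalence of copolymer hypersensitivity, and no basis for predicting extra adverse events.

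**Conclusion.** The point holds as an inconsistency between sections that bears on patient safety. The eligibility list passes a patient with known lactide/glycolide copolymer hypersensitivity, and section 15.1 contraindicates the implant in that same patient. The caprolactone wording and the difference between suspected and known mometasone intolerance are real, but they are separate and do not create the gap.

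Its size in subjects cannot be estimated from the documents. Sample size, endpoints and planned analyses are unaffected. The conclusion assumes that section 10.2 is read as it describes itself, as the full test of eligibility, and that section 7.2 correctly describes the implant as containing lactide/glycolide copolymers.

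**What to change.** The sponsor should reconcile Protocol sections 7.2, 10.2 and 15.1, together with the key criteria in the Protocol Summary, so that composition, eligibility and contraindications agree. That includes settling the status of caprolactone and using one standard for mometasone intolerance. The agreed wording should then be carried into the screening procedures. Which clinical wording is right is for the sponsor to decide, and none is proposed here.

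The cost is a short protocol clarification and a matching check of the screening materials. The SAP needs no change. Any effect on enrolment cannot be judged from the documents.
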